7.1.1.2 Inclusion/Exclusion Criteria

All inclusion and exclusion criteria will be reviewed by the investigator or qualified designee to ensure that the subject qualifies for the trial.

7.1.1.3 Medical History

A medical history will be obtained by the investigator or qualified designee. Medical history will include all active conditions and any condition diagnosed within the prior 10 years that are considered to be clinically significant by the investigator. Details regarding the disease for which the subject has enrolled in this study will be recorded separately and not listed as medical history.

7.1.1.4 Prior and Concomitant Medications Review

7.1.1.4.1 Prior Medications

The investigator or qualified designee will review prior medication use, including any protocol-specified washout requirement, and record prior medication taken by the subject within 28 days before starting the trial. Treatment for the disease for which the subject has enrolled in this study will be recorded separately and not listed as a prior medication.

7.1.1.4.2 Concomitant Medications

The investigator or qualified designee will record medication, if any, taken by the subject during the trial. All medications related to reportable SAEs and ECIs should be recorded as defined in Section 7.2.

7.1.1.5 Disease Details and Treatments

7.1.1.5.1 Disease Details

The investigator or qualified designee will obtain prior and current details regarding disease status.

7.1.1.5.2 Prior Treatment Details

The investigator or qualified designee will review all prior cancer treatments including systemic treatments, radiation, and surgeries.

7.1.1.5.3 Subsequent Anticancer Therapy Status

The investigator or qualified designee will review all new antineoplastic therapy initiated after the last dose of trial treatment. If a subject initiates a new anticancer therapy within 30 days after the last dose of trial treatment, the 30 day Safety Follow-up visit must occur before the

first dose of the new therapy. Once new anticancer therapy has been initiated, the subject will move into survival follow-up.

7.1.2 Clinical Procedures/Assessments

A visit window of ± 5 days is allowed for study visits and assessments (except as otherwise specified).

7.1.2.1 Adverse Event Monitoring

The investigator or qualified designee will assess each subject to evaluate for potential new or worsening AEs as specified in the Trial Flow Chart and more frequently if clinically indicated. Adverse experiences will be graded and recorded throughout the study and during the follow-up period according to the NCI CTCAE v4.03 (see Section 12.2). Toxicities will be characterized in terms of seriousness, causality, toxicity grading, and action taken with regard to trial treatment.

For both the TNBC and NSCLC cohorts, a safety run-in period will be implemented for the initial subjects enrolled onto the study. An initial cohort of 3 patients will be followed for toxicity through the first cycle of pembrolizumab. **The PI will submit a status update for the first 3 patients after each individual is enrolled onto this trial via a Reportable Event application.**

Please refer to Section 7.2 for detailed information regarding the assessment and recording of AEs and Section 8.0 for detailed information regarding the run-in cohorts.

7.1.2.2 Full Physical Exam

The investigator or qualified designee will perform a complete physical exam at baseline, on Days 0 and 17, every 3 weeks thereafter until completion of the protocol-specified treatment, and at EOT. Vital signs including temperature, pulse, respiratory rate, and blood pressure will be measured at each physical exam. Height will be measured at screening only. Weight will be measured at screening, on Days 0 and 17, every 3 weeks thereafter until completion of the protocol-specified treatment, at EOT, and when clinically indicated.

7.1.2.3 Directed Physical Exam

For cycles that do not require a full physical exam per the Trial Flow Chart, the investigator or qualified designee will perform a directed physical exam as clinically indicated prior to trial treatment administration.

7.1.2.4 ECOG Performance Scale

The investigator or qualified designee will assess ECOG performance status (see Section 12.1) at screening, on Days 0 and 17, every 3 weeks thereafter until completion of the protocol-specified treatment, and at EOT.

7.1.2.5 Electrocardiogram/Multigated Acquisition Scan/Echocardiogram

A 12-lead electrocardiogram ECG will be performed at screening, at EOT, and when clinically indicated. Multigated acquisition scan or echocardiogram will only be performed when clinically indicated.

7.1.2.6 Brain Magnetic Resonance Imaging

Brain magnetic resonance imaging will be performed on NSCLC patients only at screening.

7.1.2.7 Tumor Imaging and Assessment of Disease and Abscopal Effect Evaluation

Tumor assessments will be performed at screening, every 8 weeks thereafter until completion of the protocol-specified study treatment and/or at the discretion of the treating physician, when clinically indicated, and 30 days after the last dose of pembrolizumab. Tumor imaging will consist of CT scan of the chest, abdomen, and pelvis. Disease status will be assessed using RECIST 1.1 in addition to modified irRC (see Section 12). For patients with equivocal CT scan results, PET scan will be performed. For abscopal effect evaluation, CT-based response assessment (RECIST 1.1) of a non-target lesion will be performed at screening, every 8 weeks thereafter until completion of the protocol-specified study treatment, and 30 days after the last dose of pembrolizumab.

Modified irRC is based on recent cancer immunotherapy clinical studies showing that immunotherapy-mediated tumor regressions or stabilizations may only become evident or prominent over time. For this trial, the concepts of the irRC⁷⁷ are combined with RECIST 1.1 to come up with the modified irRC, which uses unidimensional measurements. For modified irRC, only target and measurable lesions are taken into account. In contrast to the RECIST 1.1, the modified irRC (a) require confirmation of both progression and response by imaging at 8 weeks after initial imaging and (b) do not necessarily score the appearance of new lesions as PD if the sum of lesion diameters of target lesions (minimum of 10 mm per lesion, maximum of 5 target lesions, maximum of 2 per organ) and measurable new lesions does not increase by $\geq 20\%$. All measurements should be recorded in metric notation. The modified irRC based on RECIST 1.1 are defined as follows:

- New measurable lesions: incorporated into tumor burden.
- New non-measurable lesions: do not define progression but precludes immune-related CR (irCR).
- Overall irCR: complete disappearance of all lesions (whether measurable or not) and no new lesions. All measurable lymph nodes must also have a reduction in short axis to 10 mm or less.
- Overall immune-related PR (irPR): $\geq 30\%$ decrease in the sum of the longest diameters of target and new measurable lesions.
- Overall immune-related SD (irSD): Sum of the longest diameters of target and new measurable lesions neither irCR, irPR, (compared to baseline), or immune-related PD (irPD) (compared to nadir).

- Overall irPD: $\geq 20\%$ increase in the sum of the longest diameters of target and new measurable lesions (compared to nadir), confirmed by repeat, consecutive observations at least 4 weeks (normally it should be done at 6 weeks) from the date first documented.

Documentation of irPD (based on the modified irRC) does not mandate discontinuation of the study treatment even after irPD is confirmed with CT scan 8 weeks after the initial observation of irPD.

RECIST 1.1 are defined as follows:

Target Lesions (Main Tumor)

- **CR:** Disappearance of all target lesions. Any pathological lymph nodes (whether target or non-target) must have reduction in short axis to < 10 mm.
- **PR:** At least a 30% decrease in the sum of the diameters of target lesions, using the baseline sum diameters as the reference.
- **PD:** At least a 20% increase in the sum of the diameters of target lesions, using the smallest sum on study (includes the baseline sum) as the reference. In addition to the relative 20% increase, the sum must also demonstrate an absolute increase of at least 5 mm. (Note: the appearance of one or more new lesions is also considered progression)
- **SD:** Neither sufficient shrinkage to qualify for PR nor sufficient increase to qualify for PD, using the smallest sum diameters while on study as the reference.

Non-Target Lesions

- **CR:** Disappearance of all non-target lesions and normalization of tumor marker levels. All lymph nodes must be non-pathological in size (< 10 mm short axis).
Note: If tumor markers are initially above the upper normal limit, they must normalize for a patient to be considered in complete clinical response.
- **Non-CR/Non-PD:** Persistence of one or more non-target lesion(s) and/or maintenance of tumor marker levels above the normal limits.
- **PD:** Appearance of one or more new lesions and/or *unequivocal progression* of existing non-target lesions. *Unequivocal progression* should not normally trump target lesion status. It must be representative of overall disease status change, not a single lesion increase.
- Although a clear progression of “non-target” lesions only is exceptional, the opinion of the treating physician should prevail in such circumstances, and the progression status should be confirmed at a later time by the review panel (or investigator).

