3.0 OBJECTIVES

3.1 Primary Objective

Objective: To determine the objective response rate (ORR) of ADV/HSV-tk plus (+) valacyclovir therapy in combination with SBRT used as a window of opportunity treatment before pembrolizumab in patients with metastatic TNBC and metastatic NSCLC. Response Evaluation Criteria in Solid Tumors (RECIST) 1.1 will be used to assess treatment response. Modified immune-related response criteria (irRC; derived from RECIST 1.1) will also be documented.

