5.1.2 Subject Inclusion Criteria

Subjects must meet all the following inclusion criteria in order to be eligible for participation in this trial:

1. Willing and able to provide written informed consent/assent for the trial.
2. Male or female ≥ 18 years of age on the day of informed consent signing.
3. Histologically confirmed locally advanced or metastatic TNBC that has relapsed on or is refractory to standard of care therapy. TNBC is defined as estrogen receptor (ER), progesterone receptor, and human epidermal growth factor receptor 2 (HER2) negative. ER and progesterone receptor negativity are defined as $<10\%$ IHC staining. HER2 test result is negative if a single test (or both tests) performed show:
 - IHC 1+ or 0
 - In situ hybridization negative based on
 - o Single-probe average HER2 copy number < 4.0 signals/cell
 - o Dual-probe HER2/CEP17 ratio < 2 with an average HER2 copy number < 4.0 signals/cell

OR histologically or cytologically confirmed metastatic NSCLC that is immunotherapy naïve or previously treated with a maximum of 1 immunotherapy regimen AND chemotherapy naïve or previously treated with 1 cycle of platinum-containing chemotherapy. *EGFR/ALK* mutation-negative NSCLC patients and NSCLC patients with *EGFR* or *ALK* genomic tumor aberrations that have failed FDA-approved targeted therapy for these aberrations will be eligible for enrollment in the study.
4. Measurable disease based on RECIST 1.1, a target lesion of suitable diameter (at least 1 cm) for SBRT with the exception of a primary breast tumor, and a non-target lesion (visceral metastatic lesion) at least 1 cm in diameter for abscopal effect evaluation.
5. Willing to provide biopsy tissues as required by the study.
6. Eastern Cooperative Oncology Group (ECOG) performance status of 0 or 1.
7. Adequate organ function as defined in Table 1. All screening labs should be performed within 28 days of trial treatment initiation.

Table 1 Adequate Organ Function Laboratory Values

System	Laboratory Value
Hematological	

Absolute neutrophil count (ANC)	≥1,500/μL (without granulocyte colony stimulating factor support within 14 days of assessment)
Platelets	≥100,000/μL
Hemoglobin	≥8 g/dL without transfusion or erythropoietin dependency (within 7 days of assessment)
White blood cell count (WBC)	>2,500/μL and <15,000/μL
Lymphocyte count	≥500/μL
Renal	
Serum creatinine	<2 X upper limit of normal (ULN)
Hepatic	

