Primary lung tumors and metastatic lesions (breast and lung) will be treated with SBRT (6 Gy X 5 fractions over 2 weeks). Primary breast tumors will be treated with three-dimensional (3D) RT (short course of 5–8 fractions over 2 weeks). Tumor target will be decided by PET/CT scan. For the planned dosing regimen, SBRT simulation will be done before treatment. For subjects with multiple tumors, the largest tumor will be selected. Sedation is not necessary for SBRT.

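### The measurable untreated lesion kept for abscopal evaluation is labelled RECIST non-target, so as written a patient can be scored PR while that lesion grows

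*Combined protocol and SAP*

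**What the plan says.** - **Endpoint.** The primary endpoint is ORR, and Section 3.1 states: "Response Evaluation Criteria in Solid Tumors (RECIST) 1.1 will be used to assess treatment response". Modified irRC is documented as well.
- **Two lesions per patient.** Criterion 4 in Section 5.1.2 asks for measurable disease, then for "a target lesion of suitable diameter (at least 1 cm) for SBRT with the exception of a primary breast tumor", and then for "a non-target lesion (visceral metastatic lesion) at least 1 cm in diameter for abscopal effect evaluation".
- **Which lesion is irradiated.** Section 5.2, under SBRT: "For subjects with multiple tumors, the largest tumor will be selected".
- **How the second lesion is read.** Section 7.1.2.7: "CT-based response assessment (RECIST 1.1) of a non-target lesion will be performed at screening". Section 3.3 uses the same label and the same criteria for the abscopal objective.
- **Response and measured progression.** Section 7.1.2.7 puts these rules under a heading that begins "Target Lesions (Main Tumor". PR is "At least a 30% decrease in the sum of the diameters of target lesions, using the baseline sum diameters as the reference". Measured PD is a rise of at least 20% and at least 5 mm in the same sum, from its smallest value.
- **Non-target progression.** It requires a new lesion or unequivocal progression. The latter is not normally to override target status, and "It must be representative of overall disease status change, not a single lesion increase". A further bullet calls clear progression of non-target lesions alone exceptional. In that case the treating physician's opinion prevails, with later confirmation by a review panel or the investigator.

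**The concern.** Criterion 4 gives every enrolled patient a visceral lesion that is large enough to measure and, given its abscopal purpose, is not irradiated. Labelled non-target in the RECIST sense, it has no part in the sum that decides PR and measured PD. What remains is the non-target route to progression, which has no size threshold and cautions against relying on one lesion.

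The gap matters most in a patient with one irradiated and one untreated lesion, because that single lesion is then all of the untreated disease. Shrinkage of the irradiated lesion alone can produce a PR. The trial is meant to show that local treatment adds to the effect of pembrolizumab, and Section 8.1 sets null response rates of 19% (TNBC) and 20% (NSCLC). A response count that can leave out growing untreated disease would favour the regimen. DoR and PFS would be affected in the same direction if they use these criteria; the documents do not define PFS.

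**Working it through.** **The plan's own figures.** No figure in the documents addresses this point. The only precision figures for ORR are the 95% margins in Section 8.1, and they reproduce with 1.96 × √(p(1−p)/n):

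- TNBC, 11/28: p = 0.393, margin 18.1 points (21.2% to 57.4%).
- NSCLC, 12/29: p = 0.414, margin 17.9 points (23.5% to 59.3%).

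They describe sampling error only and say nothing about how lesions are classified.

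**Applying the rules.** Suppose the irradiated lesion is the only target lesion and the reserved lesion is non-target.

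1. PR is decided by the irradiated lesion alone.
2. The 20%/5 mm rule is applied to the irradiated lesion alone.
3. The reserved lesion can give PD only as unequivocal progression, or through the treating physician's opinion. Neither has a number attached.
4. New lesions remain PD in either case.

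**Worked records.** Lesion sizes are assumed for illustration, at the first on-study scan, so that baseline is the smallest prior sum. The treated lesion is the larger one, as Section 5.2 requires.

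| Record | Treated, mm | Untreated, mm | Sum, mm | Treated lesion only | Both in the sum |
|---|---|---|---|---|---|
| 1 | 20 to 14 (-30.0%) | 16 to 30 (+87.5%) | 36 to 44 (+22.2%, +8 mm) | PR | PD |
| 2 | 40 to 26 (-35.0%) | 15 to 25 (+66.7%) | 55 to 51 (-7.3%) | PR | SD |
| 3 | 60 to 24 (-60.0%) | 10 to 13 (+30.0%) | 70 to 37 (-47.1%) | PR | PR |

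Records 1 and 2 change category. Record 3 does not: strong shrinkage of a large treated lesion outweighs growth of a small untreated one.

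**General form.** Let s be the fractional shrinkage of the treated lesion, g the fractional growth of the untreated one, and r the ratio of untreated to treated baseline diameter (at most 1 if the largest tumor by diameter is irradiated). The change in the two-lesion sum is (−s + r·g)/(1 + r).

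- At s = 0.30 exactly, any growth of the untreated lesion removes the PR, because the sum then falls by less than 30%.
- At s = 0.30, the sum reaches +20% when g ≥ (0.50 + 0.20r)/r. That is g ≥ 0.70 for r = 1 and g ≥ 1.20 for r = 0.5. The 5 mm condition applies in addition.

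The usual consequence of summing is therefore PR becoming SD. A move to PD needs large growth in the untreated lesion.

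**The case against.** The strongest reply is that the plan does not prevent progression from being called. A reader might infer that growth of a single non-target lesion is never PD. The text does not go that far. It asks for change that represents overall disease status, and a near-doubling of a patient's only untreated lesion could be read that way. The following bullet also lets the treating physician's opinion prevail. This part of the objection stands: the outcome is discretionary, not fixed. Discretion without a size rule, in an open-label single-arm trial, is still a weak basis for the primary endpoint.

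A second reply is that the sum may hold more than the irradiated lesion. For modified irRC, Section 7.1.2.7 allows up to five target lesions, two per organ, and the RECIST rules refer to a sum. Exclusion criterion 3 in Section 5.1.3 and the SBRT text in Section 5.2 also use *target* in a radiation sense, so *non-target* may have meant only *not irradiated*. That is a fair reading for other untreated lesions, and the documents do not settle it. It does not rescue the reserved lesion, because Sections 3.3 and 7.1.2.7 tie its non-target label to RECIST 1.1.

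Modified irRC does not close the gap either. If the reserved lesion counts as non-index, the table in Section 12.3 gives irPR for a decrease of at least 30% even with unequivocal non-index progression.

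**Conclusion.** The point holds as a matter of wording with consequences for the primary endpoint: as written, PR can be scored on the irradiated lesion while measurable untreated disease grows. The direction of the possible bias in ORR is upward. DoR and PFS follow only if they use the same criteria.

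The conclusion assumes that *non-target* is applied in its RECIST sense, that few or no other untreated lesions are in the sum, and that the physician's discretion is not used. Patients with several untreated lesions growing together, or with new lesions, are less exposed.

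A reader might go on to state how many points of ORR are at stake. The documents do not support any such figure. It would need the share of patients with one treated and one untreated lesion, the local response rate, the rate of untreated growth and the correlation between the two; none is given. Counting every patient whose untreated lesion grows would also overstate the effect, as record 3 shows. Nor can 11/28 and 12/29 serve as success thresholds for error rates: Section 8.1 uses them only to illustrate precision.

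Whether the irradiated lesion itself belongs in the sum is a separate question. Both reclassified records depend on its shrinkage, so the two effects should not be added together.

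**What to change.** In criterion 4 (Section 5.1.2) and Sections 3.3 and 7.1.2.7:

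1. Use different words for the irradiated lesion and for a RECIST target lesion.
2. Rename the reserved lesion *non-irradiated measurable lesion*.
3. State that, for endpoint scoring, it is included in the RECIST 1.1 target sum at baseline and on study, and is still reported separately for the abscopal evaluation.

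The index and non-index labels in Section 12.3 should follow the same definitions.

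No separate progression threshold for this one lesion is proposed. Such a rule would depart from the sum-based PD definition in Section 7.1.2.7 and would turn record 2 from SD into PD. It would also bear on stopping of treatment. Where progression status governs treatment (Table 2 footnote in Section 5.2, and Section 5.6), the sponsor should reconcile those passages with the clarified scoring.

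The cost is protocol wording. The lesion is already assessed on the CT scans planned every 8 weeks. The downside is that some PRs become SD or PD, so the reported ORR may be slightly lower.

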7.1.2.7.1 Second Course (Retreatment) Tumor Imaging

Tumor imaging must be performed within 4 weeks prior to restarting treatment with pembrolizumab. The first on-study imaging assessment should be performed at 8 weeks (± 7 days) after the restart of treatment. Subsequent tumor imaging should be performed every 8 weeks (± 7 days) or more frequently, if clinically indicated.

7.1.2.8 Tumor Tissue and Blood Collection and Correlative Studies

In patients with accessible tumor, biopsies will be conducted at Day 0 and 3 (\pm 2) days after the first dose of pembrolizumab. Subjects whose disease progresses while on treatment will undergo an additional biopsy before starting their new treatment. Banked tumor tissue obtained as part of the subject's standard of care and collected biopsy tissues will be evaluated for Th1 response by cytokine expression (IL-1, IL-2, IL-6, IL-12, IFN- γ , TNF- α , and GM-CSF); TILs; PD-1 and PD-L1 expression; and mutation load. PD-1 and PD-L1 expression, immune infiltrates, and cytokine expression will also be analyzed for abscopal effect evaluation.

Blood samples for correlative studies will be collected at screening, 3 (\pm 2) days after the first dose of pembrolizumab, and end of Cycle 2 of pembrolizumab. An additional sample will be collected from subjects whose disease progresses while on treatment. Blood samples will be collected into standard vacutainer tubes (2 green top tubes). Samples will be evaluated for profile of circulating suppressor and effector immunocytes and cytokines.

7.1.3 Laboratory Procedures/Assessments

Details regarding specific laboratory procedures/assessments to be performed in this trial are provided below

Laboratory Safety Evaluations (Hematology, Chemistry, and Urinalysis)

A blood sample for clinical chemistry panel (sodium, potassium, carbon dioxide, chloride, calcium, glucose, albumin, blood urea nitrogen, creatinine, total bilirubin, total protein, alkaline phosphatase, AST, and ALT) and evaluation of phosphorus, magnesium, and lactate dehydrogenase will be obtained at screening, on Days 0 and 17, and every 3 weeks thereafter until completion of the protocol-specified treatment, at EOT, and when clinically indicated. PT/INR and aPTT will be tested at screening and on Day 17. Thyroid-stimulating hormone, free thyroxine, and total triiodothyronine will be tested at screening and when clinically indicated. A blood sample for complete blood count (CBC) with platelet count and differential WBC count will be obtained at screening, on Days 0 and 17, every 3 weeks thereafter until completion of the protocol-specified treatment, at EOT, and when clinically indicated. If a patient is found to have an ANC $< 1.5 \times 10^9/L$, platelet count $< 100 \times 10^9/L$, or both, the CBC with differential should be repeated at least every other day until the ANC and platelet count have exceeded these values. For women of childbearing potential, the results of a serum β -hCG pregnancy test must be negative within 7 days before the administration of the first dose of trial treatment. If the screening serum β -hCG pregnancy test is performed more than 7 days before ADV/HSV-tk dosing, it must be repeated at baseline. Pregnancy testing is to be repeated as clinically indicated. Urinalysis (blood, glucose, protein, specific gravity) will be performed at screening and when clinically indicated. Laboratory tests for hematology, chemistry, urinalysis, and others are specified in Table 5.

Table 5 Laboratory Tests

Hematology	Chemistry	Urinalysis	Other
Hemoglobin	Albumin	Blood	Serum β - hCG†
Platelet count	Alkaline phosphatase	Glucose	PT (INR)
WBC count (total and differential)	ALT	Protein	aPTT
ANC	AST	Specific gravity	Total triiodothyronine
	Lactate dehydrogenase	Microscopic exam (If abnormal)	Free thyroxine
	Carbon dioxide	results are noted	Thyroid-stimulating hormone
	Creatinine		
	Calcium		
	Chloride		
	Glucose		
	Phosphorus		
	Potassium		
	Sodium		
	Magnesium		
	Total bilirubin		
	Total protein		
	Blood urea nitrogen		

†Perform on women of childbearing potential only.

